11.3.8 Optic Disc Examination

Optic nerve cup/disc ratio will be evaluated using a 0.0 to 1.0 scale, with larger values indicating more advanced optic nerve damage, thus a reduction from baseline is a considered an improvement. Categorical changes in cup/disc ratio from baseline will be summarized for post-baseline visits. Change from baseline at the follow-up visit (visit value – baseline values) will be categorized as an improvement of 0.2 or more (≤ -0.2), no change (> -0.2 to < 0.2), or a worsening if the ratio increases by 0.2 or more (i.e., change ≥ 0.2). The number and percentage of patients in each category will be summarized by visit and analysis cycle.

11.3.9 Lens Status and Opacification

Lens status and lens opacity assessments are performed through a dilated pupil in each eye at Screening, Baseline, Week 12, Week 24, Week 40, Week 52, Month 16, Month 20, and Month 24/Exit. Lens status is assessed as phakic, pseudophakic, or aphakic and recorded on the eCRF.

At post-Baseline visits, for eyes evaluated as phakic at Baseline, the severity of nuclear, cortical, and posterior subcapsular cataract lens opacities will be summarized (< standard photo #2, and \geq standard photo #2) in number and percentage format by visit and analysis cycle.

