12. Intraocular surgery (including cataract surgery) and/or any ocular laser surgery within the 6 months prior to treatment (Day 1)
13. Any history of corneal graft, including partial grafts (eg, Descemet's Stripping Endothelial Keratoplasty [DSEK], Descemet's Membrane Endothelial Keratoplasty [DMEK]); or incisional refractive surgery (eg, radial keratotomy), other than astigmatic keratotomy or limbal relaxing incisions
14. Corneal or other ocular abnormalities that would preclude accurate readings with an applanation tonometer, anterior segment-optical coherence tomography, specular microscope, and/or a contact pachymeter, or could confound study results, eg, moderate to severe corneal dystrophy, including Anterior Basement Membrane Disease (ABMD; ie, Map-Dot-Fingerprint [MDF]) and guttata. Mild ABMD or mild guttata are not exclusionary by clinical examination if, in the opinion of the investigator, the condition is stable and not likely to cause corneal changes during the course of the study.
15. Active or recurrent ocular disease (eg, uveitis, ocular infection, chronic moderate to severe blepharitis or severe dry eye, severe ocular seasonal allergies) or sight threatening diseases (eg, neovascular age-related macular degeneration [ARMD], diabetic macular edema) that, in the opinion of the investigator, would put the patient at a significant risk or would interfere with the interpretation of the study data. Patients with slowly progressive eye diseases (ie, mild cataracts, nonneovascular ARMD) can be enrolled at the discretion of the investigator.

16. Any history of external ocular or intraocular malignancy, and/or any history of benign ocular neoplasia that in the investigator's opinion resulted in clinically significant ocular morbidity
17. History of herpetic ocular diseases (including herpes simplex virus and varicella zoster virus)
18. The following ocular surface findings:
 - a. Bulbar conjunctival hyperemia, on either macroscopic or slit-lamp examination, $> +1$ (mild) at baseline
 - b. Active ocular surface findings other than bulbar conjunctival hyperemia, on either macroscopic or slit-lamp examination, $> +1$ (mild) at Baseline
19. History of moderate or worse ($\geq +2$) bulbar conjunctival hyperemia due to marketed prostaglandin, prostamide, or prostaglandin analog use

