20. The anticipated wearing of contact lenses during the study that deviates from the following (contact lens wear is allowed during the study, but is to be temporarily discontinued before study visits, and before and after an Administration Day according to the following):
 - a. Use of soft lenses should be discontinued at least 3 days prior to Baseline, and use of rigid gas permeable or hard contact lenses should be discontinued at least 1 week prior to Baseline
 - b. Use of soft lenses should be discontinued at least 3 days and use of rigid gas permeable or hard contact lenses should be discontinued at least 1 week prior to a scheduled study visit or Administration Day visit
 - c. Use of contact lenses of any kind should be discontinued for 1 week following any Bimatoprost SR (or Sham) administration
21. Central corneal thickness of < 480 or > 620 micrometers
22. Anticipated need for any incisional or laser ocular surgery during the study
23. History of anatomically narrow angle resulting in evidence of angle changes or any history of closed angle glaucoma. Note: historically narrow angled patients whose angle has been opened by cataract surgery or peripheral iridotomy may be eligible for enrollment if they have no evidence of angle abnormalities.
24. History or evidence of a peripheral iridotomy/iridectomy in the inferior iris

25. Any history of trabeculectomy or other types of glaucoma surgery, including a glaucoma seton or aqueous bypass stents
26. Peripheral anterior synechiae (PAS) in the inferior iridocorneal angle on gonioscopic examination at Screening
27. Visual field loss that, in the opinion of the investigator, is functionally significant (eg, split fixation, field defect within the central 10 degrees that is visually significant or likely to cause central visual impairment upon progression) or shows evidence of progressive visual field loss within the year prior to baseline (Note: Two visual fields are required for qualification, 1 performed within the 10 months prior to or at Screening, and 1 performed at baseline or during the washout period using the protocol-required testing method [see Procedure Manual]. The same test methodology should be used for all historical and study-related examination for a given patient.)
28. Evidence of macular edema during screening or in patient's medical history

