administration [Week 16], Cycle 2 Day 2 safety visit, and Cycle 2 Day 4 and Week 2 phone calls).

Contact Lenses

Use of soft contact lenses within 3 days and use of rigid gas permeable or hard contact lenses within 1 week prior to a scheduled study visit or Administration Day, or use of contact lenses of any kind within 1 week following any Bimatoprost SR (or Sham) administration in either eye is prohibited.

Other Medications

The following medications (or classes of medications) and treatment procedures are not permitted as concurrent therapy during the study unless the patient has already received nonstudy IOP-lowering medication or treatment in both eyes:

- Subconjunctival, sub-Tenon's, intravitreal, or other ophthalmic injections of any medications in either eye
- Use of any topical ophthalmic medications (except as described above and in Section 4.5.1) in either eye
- Surgical (incisional and laser) procedures that are not related to study-specific Bimatoprost SR (or Sham) and SLT administration procedures in either eye; patients may exit the study early if an ophthalmic incisional procedure is required
- Oral, intramuscular, or intravenous corticosteroids from 2 months prior to the Baseline visit through study exit
- Use of bimatoprost for hypotrichosis during the study period in either eye
- Use of cyclosporine ophthalmic solution during the study period in either eye
- Systemic use of carbonic anhydrase inhibitor
- Any initiation of or alterations in systemic regimen of beta-blocker containing medications from 2 months prior to screening through the study exit
- Use of corticosteroids in either eye (except as described in Section 4.5.1 for postoperative use) or systemically during the study or historical use prior to Baseline within:

3 years: intraocular fluocinolone acetonide
6 months: intraocular corticosteroid(s) other than fluocinolone; any injectable periocular or sub-Tenon's/subconjunctival corticosteroid
2 months: systemic (eg, oral, intramuscular, intravenous) or topical ocular corticosteroids
2 weeks: dermal corticosteroid applied to skin of the eyelid(s), around the eye, or adnexa

4.5.3 Definition of Females of (Non-)Childbearing Potential and/or Acceptable Contraceptive Methods

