8.2 BASELINE DISEASE CHARACTERISTICS

Baseline disease characteristics for each eye will be descriptively summarized by treatment of the eye for the following variables for the ITT population: diagnosis of either Open-Angle Glaucoma (OAG); primary, pseudoexfoliation, pigmentary, or Ocular Hypertension (OHT), baseline Hour 0 IOP (≤ 25 mm Hg or > 25 mmHg), iridocorneal angle Shaffer grade, and central endothelial cell density.

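### SAP 11.3.9 tabulates post-baseline lens opacity without reference to the Baseline grade and gives no rule for lenses removed on study, so new opacity cannot be read from the table

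*SAP*

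**What the plan says.** SAP 11.3.9 sets the schedule: "Lens status and lens opacity assessments are performed through a dilated pupil in each eye at Screening, Baseline, Week 12", and at later dilated visits to Month 24/Exit. It adds that "Lens status is assessed as phakic, pseudophakic, or aphakic and recorded on the eCRF". The planned analysis is that, at post-Baseline visits, "for eyes evaluated as phakic at Baseline, the severity of nuclear, cortical, and posterior subcapsular cataract lens opacities will be summarized", in two categories (below, and at or above, standard photo #2), "in number and percentage format by visit and analysis cycle". The section defines no change from Baseline, shift table or progression category. It does not say how an eye that becomes pseudophakic or aphakic is handled, or which of several visits supplies the analysis-cycle value.

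Baseline lens grade is not planned elsewhere. The eye-level list in SAP 8.2 ends with "iridocorneal angle Shaffer grade, and central endothelial cell density" and includes neither lens grade nor lens status.

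The protocol makes pre-existing opacity likely in some eyes. Under criterion 15 of Protocol 4.4, "Patients with slowly progressive eye diseases (ie, mild cataracts, nonneovascular ARMD) can be enrolled at the discretion of the investigator". It limits, but does not rule out, lens surgery during follow-up. Criterion 22 excludes "Anticipated need for any incisional or laser ocular surgery during the study". Protocol 4.5.2 bars nonstudy surgery unless both eyes have already had nonstudy IOP-lowering treatment, and adds that "patients may exit the study early if an ophthalmic incisional procedure is required".

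**The concern.** The lens table is out of line with its neighbours. Visual acuity (SAP 11.3.2), hyperemia (11.3.4), endothelial cell density (11.3.5), corneal thickness (11.3.6), slit-lamp findings (11.3.7) and cup/disc ratio (11.3.8) are all analysed against Baseline. Sections 11.3.2 and 11.3.5 also say which value represents a cycle. Section 11.3.9 does neither.

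An eye already at photo #2 on entry therefore counts the same as one that reached it after treatment. An eye that progresses far enough to be operated on has no lens left to grade, and the plan does not say where it goes. For an intracameral implant followed for 24 months, the lens question is how many eyes developed new or worse opacity. The planned table reports how many have it at a visit.

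**Working it through.** The documents state no lens-opacity rate, so there is no plan figure to reproduce. Every rate below is an assumption, chosen to show how the table behaves.

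**Step 1: no lenses removed.** Let b be the share of baseline-phakic eyes at or above photo #2 at Baseline, and p the share of the remaining eyes that reach it. The planned table shows b + (1 − b)p. Take p = 10% in Bim SR eyes and 5% in SLT eyes, a true ratio of 2 among eyes at risk.

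| b | Bim SR eyes | SLT eyes | Difference | True excess, (1 − b) × 5 points |
|---|---|---|---|---|
| 20% | 28.0% | 24.0% | 4.0 points | 4.0 points |
| 30% | 37.0% | 33.5% | 3.5 points | 3.5 points |
| 40% | 46.0% | 43.0% | 3.0 points | 3.0 points |

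The absolute excess over all phakic eyes is preserved exactly. The incidence (10% and 5%) is not shown, and at b = 30% the ratio reads 37.0/33.5 = 1.10 instead of 2.

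**Step 2: some progressing eyes operated on.** Let s be the share operated on and suppose half the progressing eyes are, so s = (1 − b)p/2. At b = 30%, s is 3.5% in Bim SR eyes and 1.75% in SLT eyes. The result depends on a rule the SAP does not give:

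- Removed eyes leave the denominator, (b + (1 − b)p − s)/(1 − s): 0.335/0.965 = 34.7% versus 0.3175/0.9825 = 32.3%, a difference of 2.4 points.
- Removed eyes stay in the denominator but not in the numerator: 33.5% versus 31.75%, a difference of 1.75 points.
- The last grade before surgery is kept: 37.0% versus 33.5%, a difference of 3.5 points.

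The same data give differences from 1.75 to 3.5 points according to an unstated convention. With eyes leaving the denominator, b = 20% gives 25.0% versus 22.4%, and b = 40% gives 44.3% versus 42.1%.

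**Step 3: what a baseline-referenced table adds.** Take 115 phakic eyes in one treatment group (80% of the 144 planned evaluable patients, the 80% being assumed). Suppose 29 are at or above photo #2 at Baseline (25.2%), 9 are new, and 7 of the 29 have the lens removed. If removed eyes leave the denominator, the planned table shows (29 + 9 − 7)/(115 − 7) = 31/108 = 28.7%. The proposed rows show 9/(115 − 29) = 9/86 = 10.5% newly at or above photo #2, 7/115 = 6.1% with lens removal, and 16/115 = 13.9% with either.

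**The case against.** Three parts of the opposing case stand.

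- **The contrast between treatments is not destroyed.** Each patient supplies one eye per treatment and the primary eye is randomized (Protocol 5.4), so pre-existing opacity should be similar in both columns. Step 1 confirms that mixing it in leaves the absolute difference intact.
- **The SAP does not say that operated eyes drop out.** A reader might infer this, since a removed lens cannot be graded, but the text is silent. An eye graded before surgery could still count in the by-cycle summary, and SAP 17.5 uses all post-baseline assessments for safety evaluation and lists them. The defect is the missing rule.
- **Pre-existing opacity is bounded.** Only mild cataract is let in, visual acuity must be 20/50 or better (Protocol 4.3), and anticipated surgery is excluded. Nothing in the documents supports a particular baseline share.

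A reader might also infer that worsening could be displayed as improvement. In the 115-eye example, if removed eyes leave the denominator, the share falls below its Baseline value only when removals from the 29 eyes exceed 9/(1 − 29/115) = 12.0. With a fixed denominator they must exceed 9. Across assumed values of 60–100% phakic, 10–40% at or above photo #2 at Baseline and 5–10% new, the break-even is about 4 to 15 removals per group. No removal rate is documented and surgery is restricted, so the documents do not support this as an expected result.

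Other displays give partial cover. Ocular adverse events are tabulated by eye, class, term and severity (SAP 11.1), and acuity line change is measured from Baseline, but neither uses the graded lens examination. Protocol 6.2 includes the lens in biomicroscopy, and SAP 11.3.7 counts increases from Baseline of at least 2 grades. However, SAP 11.0 and Table 17-1 list lens assessment separately from biomicroscopy, and the 11.3.7 grades (0.5, 1, 2, 3) are not stated to apply to photo-based lens grades. That cover is uncertain.

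**Conclusion.** The concern holds in limited form. SAP 11.3.9 plans a prevalence table with no Baseline reference, no rule for lens removal and no rule for the cycle value. The incidence and ratio of new opacity cannot be read from it, and eyes that progress to surgery may be lost from later visits. The between-eye difference in percentage points is sound if no lenses are removed. Otherwise it depends on the unstated convention (1.75 to 3.5 points in the worked case at b = 30%).

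The actual size cannot be set, because baseline opacity, progression and surgery rates are all assumed here. The table is descriptive, carries no hypothesis test and does not touch the primary result. Priority: a minor safety-display improvement.

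**What to change.** In SAP 11.3.9:

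- For each opacity type and treatment eye, tabulate the number and percent of eyes phakic and below photo #2 at Baseline that reach photo #2 or above at any post-baseline visit, overall and by analysis cycle.
- Show on-study change from phakic to pseudophakic or aphakic as its own row, and count it as progression in a combined row. State the denominator of each row; all baseline-phakic eyes would suit these two.
- Add the Baseline grade by treatment eye.
- Keep the by-visit split as a supporting table, with a stated rule for eyes that can no longer be graded.

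The cost is SAP wording and one more safety table; grades and lens status are already collected. The downside is that lens removal for reasons other than progression enters the combined row, which the separate row makes visible. Two limits remain. Worsening that stays on one side of photo #2 is not counted as new opacity, and a lens removed after early exit may never be recorded as a status change.

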11.3.10 Gonioscopy and Bim SR Implant Assessment

Gonioscopy is performed to assess the inferior iridocorneal angle and the Bim SR implant in all study visits except SLT and Bim SR administration days for all patients.

If an implant is visible, visible implant size is to be recorded on eCRF as a percentage of the original material (0-25, 26-50, 51-75, 76-100, 101-125, 126-150, 151-200, >200). Number and percentage of patients with any implant visible during the study will be summarized in a tabular format. In addition, number and percentage of implants visible will also be summarized during each study period for Bim SR eye further breaking down by the categorical percentage visible of each implant. Also, the number and percentage of patients who have any implant(s) in contact with corneal endothelium at any visit within a cycle will be summarized by analysis cycle.

12.0 SUBGROUP ANALYSES

Subgroup analyses will be conducted for patients who received the Bim SR 10 μ g administration under the flexible dosing regimen as specified in the protocol amendment 6 regardless of the visit at which patients received the second Bim SR 10 μ g administration. It will include patients enrolled under amendment 6 or patients re-consented to amendment 6 before receiving the second Bim SR 10 μ g administration. Otherwise, patients will be classified in the fixed dosing regimen subgroup.

In addition, subgroup analysis by the disease diagnosis, open-angle glaucoma (OAG) or ocular hypertension (OHT) at screening, will be performed on IOP data.

12.1 IOP CHANGE FROM BASELINE

The primary efficacy analysis in Section 10.1 will be performed for the ITT and PP populations for the flexible administration regimen.

For the OAG and OHT subgroups, baseline IOP and IOP change from baseline will be summarized for the ITT population.

12.2 TIME TO SECOND BIM SR ADMINISTRATION

For patients who received 2 Bim SR 10 μ g administrations under the flexible dosing regimen, the time from the first to the second administration will be analyzed using Kaplan-Meier (KM) method with graphical displays:

- Time to the second administration of Bim SR= (Date of the second administration of Bim SR 10 µg – Date of the First Bim SR 10 µg) +1.

In the calculation, if a patient did not receive the second Bim SR by Month 12 as specified in the study protocol, then the patient will be censored at Month 12 unless the patient withdrew early or received non-study IOP treatment prior to Month 12 visit which ever occurred first.

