1.2.3 Clinical Studies with Bimatoprost SR

Study 192024-041D was a phase 1/2 paired-eye comparison study evaluating the safety and efficacy of 4 dose strengths of Bimatoprost SR (6, 10, 15, or 20 µg [2 x10 µg implants]), as single or repeat administrations in 1 eye (study eye), versus the use of topical LUMIGAN 0.03% once daily in the contralateral eye (nonstudy eye). The objective of this study was to evaluate the safety and IOP-lowering efficacy of Bimatoprost SR in patients with OAG.

A total of 109 patients received at least a single administration of Bimatoprost SR, and 24 patients received a repeat administration of Bimatoprost SR. A trend in dose response was observed across the 4 dose strengths that were tested.

Data suggest that the implant may provide topical prostaglandin analog-like efficacy up to 3 to 4 months post-implantation in the majority of patients. Data following the second administration in the retreated patients showed similar IOP lowering efficacy to that observed following the first administration of Bimatoprost SR. In addition, efficacy was maintained longer than the expected 3- to 4-month duration in many patients in this completed study. By Month 6, most patients (> 66%) were still maintained on monotherapy with the initial Bimatoprost SR implant administered. Among all Generation 2 dose strengths, at least 33% of patients had not received rescue or a second Bimatoprost SR treatment by Month 12. At Month 24, at least 23% of patients had not received rescue or a second treatment.

Bimatoprost SR showed an acceptable safety profile with single and repeat administrations in study 192024-041D. Most adverse events were ocular, mild or moderate in severity, occurred within the first 2 days after Bimatoprost SR administration, and were considered related to the study drug administration procedure. There were no reports of serious study drug-related adverse events, and no new safety concerns were observed after the second treatment. Please refer to the Investigator's Brochure for details on reported safety findings.

Two identical global phase 3 studies (Studies 192024-091 and 192024-092) were initiated in late 2014. These studies are assessing the safety and efficacy of Bimatoprost SR in multicenter, randomized, masked, parallel-group comparison studies of 2 dose strengths of Bimatoprost SR (10 and 15 µg) to an active control (timolol maleate 0.5%).

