4.5.2 Prohibited Medications/Treatments

The decision to administer a prohibited medication/treatment is taken with the safety of the study participant as the primary consideration. When possible, Allergan should be notified before the prohibited medication/treatment is administered.

During the study, patients must not participate in other investigational drug or device studies.

Nonstudy IOP-lowering Treatments

Any concurrent nonstudy IOP-lowering treatment (eg, topical ophthalmic medication containing an ocular antihypertensive, LT) is prohibited in either eye during the study (through Month 24), unless necessary for the safety of the patient due to inadequate control of IOP as determined by the investigator. Inadequate control of IOP should be confirmed at a subsequent visit (scheduled or unscheduled visit). Initiation of treatment in one eye should not automatically lead to initiation of treatment in the contralateral eye. Each eye should be evaluated on an individual basis when determining the need for additional nonstudy IOP-lowering treatments. If nonstudy IOP-lowering treatment is initiated, the investigator will be expected to attest to the need for additional nonstudy IOP-lowering treatment for safety reasons for each eye individually. Use of any concurrent nonstudy IOP-lowering treatment with any known effect on study outcomes (eg, crossover effect on the contralateral eye) is prohibited during the study.

In order to maintain patient masking to treatments assigned to each eye, patients who have received nonstudy topical IOP-lowering treatment in a Bimatoprost SR eye will receive Sham Bimatoprost SR administration in that eye on the Bimatoprost SR Cycle 2 administration day(s). If nonstudy topical IOP-lowering medication is initiated in an SLT eye, the patient will continue to receive Sham Bimatoprost SR administration in the SLT eye on the administration day(s). In all cases, the contralateral eye that does not require nonstudy topical IOP-lowering medication will maintain the same treatment regimen assigned at randomization. Patients who have received nonstudy IOP-lowering treatment in both eyes will not receive Bimatoprost SR administration or Sham Bimatoprost SR administration in either eye, and therefore do not need to attend the Bimatoprost SR (or Sham Bimatoprost SR) administration visits and immediate postadministration visits (ie, Bimatoprost SR Cycle 2

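### SAP 12.2 names an analysis set with nobody to censor, and its censoring rule, applied to all flexible-regimen patients, inflates the apparent share given a second implant

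*SAP*

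**What the plan says.** SAP 12.2 opens its analysis set with "For patients who received 2 Bim SR 10", meaning those given two 10 µg implants while on the flexible regimen. It then says that "the time from the first to the second administration will be analyzed using Kaplan-Meier (KM) method with graphical displays". The following paragraph turns to the opposite case, a patient with no second implant by then, and its instruction is: "then the patient will be censored at Month 12 unless the patient withdrew early or received non-study IOP treatment prior to Month 12 visit". The earlier of these dates applies. The rule does not say which eye the treatment was in. No competing-risk method is named, and the quantity that the curve should estimate is not stated.

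The protocol settles what rescue means for a second implant.

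- **Bim SR eye rescued.** Protocol 4.5.2: "patients who have received nonstudy topical IOP-lowering treatment in a Bimatoprost SR eye will receive Sham Bimatoprost SR administration in that eye". Protocol 5.9.1.5 says the same. After rescue in both eyes there are no further administration visits.
- **SLT eye alone rescued.** Protocol 4.5.2: "the contralateral eye that does not require nonstudy topical IOP-lowering medication will maintain the same treatment regimen assigned at randomization". Protocol 5.9.1.5 keeps such patients attending administration visits, and rescued patients are followed to Month 24. A second implant stays possible, and it would be observed.

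**The concern.** There are three difficulties.

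1. **The set contradicts the rule.** If only patients with two implants enter, there is no non-recipient to censor.
2. **The cut at SLT-eye rescue is one-sided.** Once non-recipients are included, a patient whose SLT eye is rescued and whose Bim SR eye is re-implanted later counts as an event on the implant date. A patient with the same rescue and no later implant is cut back to the rescue date. Censoring then depends on the future outcome, and only event-free time leaves the risk set.
3. **Bim SR-eye rescue is treated as neutral censoring.** Under the protocol it rules out a second implant. Kaplan-Meier instead lets the censored eye stand for eyes that could still be re-implanted.

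At stake is the figure most readers would take from this display: the proportion needing a second implant by Month 12 under the regimen that Amendment 6 introduced.

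**Working it through.** SAP 12.2 states no figure, so there is none to reproduce. Every rate below is an assumption, except the Month 12 figure from the earlier phase 1/2 study, which is used only for illustration.

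**Step 1: the set as written.** All members have two implants, so all have events. There is no censoring, and the curve ends at 100% whatever the true proportion is.

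**Step 2: one-sided cut, by hand.** Take 100 patients, of whom 50 are re-implanted at Week 16 and none later. SLT-eye rescue precedes Week 16 in 10 recipients and 10 non-recipients.

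- Actual proportion: 50/100 = 50%.
- Rule as worded (only the 10 non-recipients are cut): 50/90 = 55.6%.
- Censoring both groups alike: 40/80 = 50%.

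The asymmetry alone creates the error.

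**Step 3: competing event, by hand.** Take 100 patients. Ten have Bim SR-eye rescue before Week 16, and 45 of the other 90 are re-implanted then. One minus Kaplan-Meier is 45/90 = 50%; the proportion re-implanted is 45/100 = 45%.

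**Step 4: competing event, closed form.** Of the phase 1/2 study, Protocol 1.2.3 says that "at least 33% of patients had not received rescue or a second Bimatoprost SR treatment by Month 12". Take 33% as the event-free share, assume proportional cause-specific hazards, and let s be the share of events that are second implants (the protocol does not give the split). Then cumulative incidence = 0.67 × s, and one minus Kaplan-Meier = 1 − 0.33^s.

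| s | Cumulative incidence | 1 − KM | Excess (points) |
|---|---|---|---|
| 0.9 | 60.3% | 63.1% | 2.8 |
| 0.7 | 46.9% | 54.0% | 7.1 |
| 0.5 | 33.5% | 42.6% | 9.1 |
| 0.3 | 20.1% | 28.3% | 8.2 |

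**Step 5: simulation, 400,000 patients per scenario.** Half are re-implanted at Week 16 and 30% of the rest by Month 12. Rescue times are exponential, independent of each other and of retreatment. Bim SR-eye rescue blocks a later implant. There are no withdrawals.

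| Rescue by Month 12 (Bim SR eye / SLT eye) | Cumulative incidence | KM, Bim SR-eye rescue censors | KM, rule as worded |
|---|---|---|---|
| 5% / 5% | 63.7% | 65.0% | 65.5% |
| 10% / 20% | 62.3% | 64.9% | 67.3% |
| 20% / 30% | 59.6% | 64.9% | 68.8% |
| 0% / 10% | 65.0% | 65.0% | 66.1% |
| 0% / 20% | 65.0% | 65.0% | 67.4% |
| 0% / 30% | 65.0% | 65.0% | 68.9% |

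From the first three rows, the excess is 65.0 − 63.7 = 1.3 to 64.9 − 59.6 = 5.3 points from Bim SR-eye rescue alone. Under the rule as worded it is 65.5 − 63.7 = 1.8 to 68.8 − 59.6 = 9.2 points. In the last three rows, censoring recipients and non-recipients alike at SLT-eye rescue returns 65.0%.

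**Step 6: a different target.** Suppose the aim is the probability of re-implantation had rescue not existed, and that rescue and retreatment share a cause (log-normal frailty). Kaplan-Meier is then too low: 57.0% against 58.7% (frailty SD 1.0, nominal 20% Bim SR-eye rescue), and 51.6% against 54.7% (SD 1.5, 30%). The cumulative incidences in those two cases are 53.1% and 47.2%, so one minus Kaplan-Meier still exceeds the proportion actually re-implanted.

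**The case against.** **On the stated set neither rescue fault operates.** True. The 100% endpoint comes from selecting on the outcome. But a rule for non-recipients has no purpose unless they are meant to be included, so the two sentences must be reconciled, and the rule matters once they are.

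**The missing eye may be only loose drafting.** SAP 10.0, 10.1, 10.2.2 and 17.1 all tie rescue to the eye concerned, and each patient has one Bim SR eye. If SAP 12.2 means treatment of that eye, the one-sided cut disappears and only the competing-event issue remains. That stands. The wording of 12.2 does not say it, though, and its unit is the patient.

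**Censoring at rescue is a legitimate choice of target.** Partly right. Censoring at Bim SR-eye rescue leaves the cause-specific hazard of re-implantation unbiased, and SAP 10.1 adopts a hypothetical strategy for rescue in the primary analysis. SAP 12.2 names no such target, so the natural reading of the curve is the proportion re-implanted.

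**The excess may be lost in sampling error.** The size of the flexible subgroup is not stated. With an assumed 80 to 160 patients, a 95% interval around 55% is about ±11 to ±8 points, wider than the 1 to 5 points. That limits the importance of the fault, but the fault is systematic and costs little to remove.

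A reader might also infer that the plan conceals rescue in the Bim SR eye. It does not: SAP 10.2.2 plans Kaplan-Meier time to rescue for Bim SR and for SLT, and again from the second implant, and SAP 8.4.2 tabulates non-study IOP-lowering medication by eye. Neither is split by regimen, but both include the flexible-regimen patients.

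**Conclusion.** The point holds in a limited form and is minor. SAP 12.2 contradicts itself on who is analysed. If its censoring rule is applied to all flexible-regimen patients, one minus Kaplan-Meier overstates the proportion re-implanted by Month 12 whenever non-recipients are rescued earlier. The excess is about 1 to 5 points for 5% to 20% Bim SR-eye rescue, and about 2 to 9 points if SLT-eye rescue of 5% to 30% also censors. Neither range is a bound: the closed form gives up to 9.1 points from Bim SR-eye rescue alone when rescue makes up more of the events. The documents give no rescue or retreatment rates for this trial, so the real size is unknown and could be small.

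It would be tempting to say simply that the re-administration rate is overstated. The documents do not support that without qualification. The direction applies to the cumulative proportion. It does not apply to the cause-specific hazard under Bim SR-eye censoring, and it can reverse for a no-rescue target. Nor does the point reach the trial's conclusions: this is a descriptive subgroup analysis with no test, and the primary noninferiority and superiority analyses do not use it.

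**What to change.** In SAP 12.2:

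1. Define the set as all flexible-regimen patients (as classified in SAP 12.0) who received a first Bim SR 10 µg implant.
2. Name the Bim SR eye wherever the rule refers to non-study IOP-lowering treatment.
3. Do not censor at rescue of the SLT eye alone; follow to the second implant, Bim SR-eye rescue, withdrawal or Month 12.
4. Report the cumulative incidence of second administration, with rescue of the Bim SR eye (alone or with the SLT eye) as the competing event.

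Time to the first of second implant or Bim SR-eye rescue would be an optional addition, closer to how Protocol 1.2.3 summarises the phase 1/2 study.

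The cost is a few lines of SAP text and one standard procedure. No new data are needed and no treatment rule changes. The reported proportion will be somewhat lower than the Kaplan-Meier figure if any rescue occurs before Month 12 in non-recipients.
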